**6.2.4.5. Week 4 Visit**

- 6.2.4.5.1. At 4 week visit, vitals will be taken, pill count will be performed, MAAS and HIV-SI surveys completed. Followed by history, symptom based physical, and laboratory exam. Patient will be given 90-day supply of study drug.

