#### 4.2.1. Primary Endpoint:

4.2.1.1. Change in adherence from baseline to 4 months, measured by adherence surveys

#### 4.2.2. Secondary Endpoints:

4.2.2.1. Change at 4 months from baseline in tolerability measured by standardized patient reported outcome questionnaire

4.2.2.2. Proportion of subjects that have HIV-1 RNA  $\geq$  50 copies/mL at baseline and at Week 16

4.2.2.3. Proportion of subjects with significant changes at 4 months from baseline in serum creatinine, AST or ALT

4.2.2.4. Change at 4 months from baseline in absolute and percentage CD4.

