4.2.2.5. Change at 4 months from baseline in absolute and percentage weight

4.2.2.6. Number of drug discontinuation for any reason

4.2.2.7. Compare adherence measured by adherence surveys on week 4 and Week 16 to the pill counts from week 4 and Week 16.

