6.1.3.1.2. HIV positive receiving ART of any type

**6.1.3.2. Exclusion criteria**

6.1.3.2.1. Inability to read/respond to questions written in English OR Spanish

**6.1.4. Study Procedure**

6.1.4.1. During patient triage, all patients who are HIV positive and currently prescribed anti-viral therapy will be offered participation in completing the Midland ART Adherence Survey (MAAS, Appendix 1). They will be provided a paper copy of the Study consent and the survey with a clipboard and a pen and allowed to self-complete it during the triage process. If they opt-in to the survey, they will turn in the completed surveys to staff members who will (1) determine if patient is eligible for Part II of study and (2) share the results with the provider, if subjects indicate they would like them shared. For those who opt out, no demographic data will be collected.

6.1.4.2. Survey sheets will not contain any Personal Identifying Information (PII). The results of the survey will be entered into a spreadsheet and analyzed at the completion of the enrollment period.

6.1.4.3. Subjects will be offered enrollment in Part 1 until target enrollment in part 2 has been completed or until subject sample population has been offered participation, whichever comes first.

## 6.2. Part 2

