**6.2.4.7. Week 16 Visit**

- 6.2.4.7.1. At 16 week visit, subjects will have vitals taken, pill count will be performed; both the MAAS and HIV-SI will be completed, followed by history, symptom based physical, and laboratory exam. Pill count will be taken from bottle dispensed at baseline visit. Staff will confirm with patient that they have the commercial medication .

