## 8.6. Part 2 –

### 8.6.1. Primary Endpoint

- 8.6.1.1. Percentage of subjects reporting suboptimal adherence, analyzed by intention to treat, from baseline to four-months using Rasch scores. The hypothesis testing will be carried out at the 5% (2-sided) significance level unless otherwise specified. P-values will be rounded to three decimal places. P-values less than 0.001 will be reported as <0.001 in tables. P-values greater than 0.999 will be reported as >0.999.
- 8.6.1.2. We hypothesize that a minimum of 85% of subjects taking DRV/COB/FTC/TAF will demonstrate optimal adherence from baseline to four-months as measured by the Midland ART Adherence Survey. Optimal adherence is defined as a Rasch score greater than or equal to 90%. Rasch scores range from 0% (no adherence) to 100% (perfect adherence).

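### At Weeks 4 and 16 the protocol lists the pill count ahead of the adherence survey, and nothing shields the self-report from the count

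*Protocol*

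**What the plan says.** Protocol section 6.2.4.5.1 describes Week 4 as "At 4 week visit, vitals will be taken, pill count will be performed, MAAS and HIV-SI surveys completed", and continues "Followed by history, symptom based physical, and laboratory exam". Section 6.2.4.7.1 describes Week 16 in the same order: "subjects will have vitals taken, pill count will be performed; both the MAAS and HIV-SI will be completed, followed by history".

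The MAAS is the primary instrument of Part 2. Section 4.2.1.1 defines the primary endpoint as "Change in adherence from baseline to 4 months, measured by adherence surveys". Section 8.6.1.2 adds the hypothesis: "We hypothesize that a minimum of 85% of subjects taking DRV/COB/FTC/TAF will demonstrate optimal adherence from baseline to four-months". Optimal means a Rasch score of at least 90% on the MAAS.

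Section 4.2.2.7 sets a secondary endpoint that depends on both measures: "Compare adherence measured by adherence surveys on week 4 and Week 16 to the pill counts from week 4 and Week 16".

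Before the switch the setting is different. Under section 6.1.4.1, Part 1 subjects receive the MAAS on paper and are "allowed to self-complete it during the triage process"; section 6.1.4.2 keeps personal identifiers off the sheet. Table 6.2.4.1.2 and Appendix 5 also mark a MAAS at the Part 2 screening or combined visit. The adherence and accountability row of Table 6.2.4.1.2 is marked only at Weeks 4 and 16.

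**The concern.** Questions 8 to 10 of the MAAS ask how often doses are missed, including days missed in the last week and the last month. A tablet count addresses much the same matter. If it comes first, the subject answers those questions shortly after staff have dealt with the objective record of the same behaviour.

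Two uses of the survey are exposed. First, the primary endpoint compares the MAAS across the switch. A step that precedes the survey only after the switch is a change in measurement conditions, and with no control arm its effect, if any, is mixed with the effect of the drug. Second, 4.2.2.7 asks whether the survey agrees with the pill count. If the count can inform the answers, some of the agreement may come from the order of steps, yet it could be read as evidence that the self-report is accurate.

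**Working it through.** No figure in the protocol depends on the order of steps, so there is nothing to reproduce. The check sets the sections side by side.

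**1. Is the count placed before the survey?** At both visits the list runs: vitals, pill count, MAAS and HIV-SI, then history, symptom-based examination and laboratory tests. Both texts use sequencing words to put history and examination after the group. The baseline text (6.2.4.4.2) also describes its steps in time order. Reading the Week 4 and Week 16 lists as sequences is therefore natural, though no sentence says that the MAAS must wait for the count.

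**2. Does anything override that order or guard against its effect?** Table 6.2.4.1.2 and Appendix 5 show which procedures belong to which visit, but give no order within a visit. No section says that the survey is handed in first, that tablets are counted away from the subject, or that the result is held back until the survey is complete.

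**3. Do conditions differ across the switch?**

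| MAAS occasion | Pill count listed before it? | Feeds the 4-month primary endpoint? |
|---|---|---|
| Part 1, at triage | No | Before the switch |
| Part 2 screening or combined visit | No | Before the switch |
| Week 4 | Yes | No |
| Week 16 | Yes | Yes |

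A count is listed ahead of the MAAS at 2 of 2 scheduled on-treatment visits and at no visit before the switch. Only Week 16 bears on the primary endpoint. Both visits bear on 4.2.2.7.

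**4. How close is the overlap of content?** At Week 4 the count covers roughly the period that question 10 asks about. At Week 16 the overlap is less clear: section 6.2.4.7.1 takes the count from the bottle dispensed at baseline, a 30-day supply, although section 6.2.4.5.1 dispenses a 90-day supply at Week 4. As written, that count would cover a different period from questions 9 and 10. The two passages must be reconciled in any case, since 4.2.2.7 uses this count; that is a separate point.

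**5. Can a size be given?** No. The documents contain nothing on how many subjects would answer differently after a count, or in which direction.

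**The case against.** The strongest reply is that the order is only inferred. The pill count and the surveys are joined by commas or a semicolon, and the sequencing words govern only what follows the group. Where the author wanted a step before a survey, as with vitals before the HIV-SI at baseline, the text says so. This stands in part: the reading is natural, not compelled. But no text supports the opposite order, and a site following the list would count first.

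A reader might infer that subjects see the count and adjust their answers to it, so that the primary result is biased in favour of the drug. The documents do not support that. They do not say that the subject watches the count or hears its result. Direction is also open: a count beforehand could prompt more candid answers and lower the scores after the switch.

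A reader might also try to attach a number by supposing that a few of the 30 subjects cross the missed-dose boundary in questions 8 to 10. That boundary is the Part 2 entry rule (6.2.3.1.1.2), not the response definition, which is a Rasch score of at least 90%. Crossing one does not establish crossing the other, and any number of subjects chosen would be arbitrary.

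Nor is 4.2.2.7 the only evidence on adherence. The percentage of subjects at 90% or more by pill count (8.2.2.2.2) does not depend on the survey, and HIV-1 RNA is an objective though indirect correlate. What 4.2.2.7 offers is the direct comparison of the survey with another adherence measure, and that comparison is what the order leaves exposed.

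Finally, section 5.5.1 tells subjects to bring their medication to each visit, so they may expect a count whatever the order. This stands, and it limits what re-ordering can achieve.

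**Conclusion.** The point holds as an unguarded risk to measurement. On the natural reading of 6.2.4.5.1 and 6.2.4.7.1, the pill count comes before the MAAS at both on-treatment visits and before no MAAS prior to the switch, and nothing protects the self-report from it. The conditions of the primary instrument may therefore differ between baseline and Week 16, and the comparison in 4.2.2.7 is not protected from procedural agreement at Week 4 or Week 16.

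It is not a demonstrated bias. Size and direction are unknown, and no percentage-point figure should be attached. The conclusion assumes that sites carry out the steps in the order listed. The protocol gives no reason for counting first, and the remedy is nearly free, so the change is worth making.

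**What to change.** In sections 6.2.4.5.1 and 6.2.4.7.1, re-order the steps so that the MAAS and HIV-SI are self-completed and handed in before any tablets are counted. Add one sentence stating that survey answers are not altered after the count. If tablets are counted at an early discontinuation visit, the same order can apply there.

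The cost is the rewording of two short paragraphs and a word to site staff. Procedures, visits and sample size are unchanged. Because subjects may still expect a count, the change lessens the difference in conditions across the switch without removing it, and the study report should say so when it interprets the primary result and 4.2.2.7.

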**6.2.4.6. Week 14 Event**

- 6.2.4.6.1. A script for commercial study drug will be sent to the patient's pharmacy of choice approximately 2 weeks prior to week 16 visit to ensure uninterrupted ART for the patient. Staff will confirm with patient that medication will be available to them via pharmacy prior to 16 week visit.

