### 5.3. Dosage and Administration

**5.3.1.** Study drug will be dosed as one tablet taken orally once daily with food in adults. For subjects who are unable to swallow the whole tablet, it may be split into two pieces using a tablet-cutter, and the entire dose should be consumed immediately after splitting.

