**5.5. Accountability for Study Drug**

**5.5.1.** Subjects will be instructed to bring all study medication in the original container at each clinic visit for drug accountability. The Investigator will be responsible for maintaining accurate records for all study drug bottles dispensed and tablets returned. Study medication supplies, including partially used or empty bottles, must be accounted for by the investigator prior to destruction or return.

**5.5.2.** The Investigator is responsible for ensuring adequate accountability of all used and unused study drug. This included acknowledgement of receipt of each shipment of study drug (quality and condition). All used and unused study drug dispensed to subjects must be returned to the site.

**5.5.3.** Study Drug accountability records will include:

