#### 6.2.4. Study Procedure

##### 6.2.4.1. Overview

6.2.4.1.1. Subjects who are referred for screening from Part I who meet other eligibility criteria (see table 6.2.4.2.1) will be offered enrollment in Part 2. Those who provide consent will complete HIV Symptom Index (HIV-SI), a validated Patient Reported Outcome survey to assess side effects/quality of life, undergo physical and laboratory examinations, and ART will be switched to DRV/COB/FTC/TAF (Syntuza). For subjects who were not suppressed at their last lab evaluation, an HIV genotype will be performed prior to enrollment. Subjects who do not provide consent to enroll in the study will be referred back to their provider to address issues with tolerance and adherence.

6.2.4.1.2. Subjects will be followed for 16 weeks. During that period, they will be brought back for evaluation at the 4th and 16th week. At those evaluations, they will again complete the PRO and adherence surveys to assess tolerability and adherence. At the evaluations, they will also be monitored for safety and effectiveness via physical exams and laboratory studies. See Table 6.2.4.1.2

6.2.4.1.2.1. Labs at each visit: Complete Blood Count, Complete Metabolic Panel, Urinalysis, CD4 panel, HIV1 Quantitative viral load. If subject is of childbearing potential, urine pregnancy will be performed.

6.2.4.1.2.1.1. Special situations: If HIV viral load is >200 prior to baseline and not accompanied by recent genotype, a genotype will be performed.

6.2.4.1.3. Interim analysis will be performed when all subjects have completed 1 month evaluation or when 10 subjects have completed 4 month evaluation, whichever comes first.

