**6.2.4.4. Baseline Visit**

- 6.2.4.4.1. If required labs have been performed within 30 days baseline may be performed same day and self-completed HIV Symptom Index (HIV-SI, Appendix 2) survey will be completed, baseline labs will be drawn and patient will be given 30 day supply of study drug.
- 6.2.4.4.2. If baseline is not done same day: vitals will be taken prior to HIV-SI survey being completed. Then updated history and symptom based physical will be performed and baseline labs will be drawn. Patient will be given 30 day supply of study drug; first dose will be taken in office.

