#### 8.2.2.1. Primary Endpoint

8.2.2.1.1. Percentage of subjects reporting suboptimal adherence, analyzed by intention to treat, from baseline to 16 weeks.

8.2.2.1.1.1. *We hypothesize that a minimum of 85% of subjects taking DRV/COB/FTC/TAF will demonstrate an optimal adherence score from baseline to four-months as measured by the Midland ART Adherence Survey.* Optimal adherence is defined as a Rasch score greater than or equal to 90%. Rasch scores range from 0% (no adherence) to 100% - (perfect adherence).

8.2.2.2. Secondary Endpoints. These are descriptive endpoints so no hypotheses are tested.

8.2.2.2.1. Change at 4 months from baseline in tolerability measured by standardized patient reported outcome questionnaire

8.2.2.2.2. Percentage of subjects with greater than or equal to 90% by pill count

8.2.2.2.3. Proportion of subjects that have HIV-1 RNA  $\geq 50$  copies/mL at baseline and at month 4

8.2.2.2.4. Proportion of subjects with significant changes at 4 months from baseline in serum creatinine, AST or ALT

8.2.2.2.5. Change at 4 months from baseline in absolute and percentage CD4.

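### Once the Week 16 pill count is reconciled to include the Week 4 supply, any dose taken from the pre-arranged commercial bottle will read as a missed dose

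*Protocol*

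**What the plan says.** Dosing (5.3.1): "Study drug will be dosed as one tablet taken orally once daily with food in adults". Follow-up (6.2.4.1.2): "Subjects will be followed for 16 weeks". Study drug is issued twice. At baseline (6.2.4.4.2): "Patient will be given 30 day supply of study drug; first dose will be taken in office". At Week 4 (6.2.4.5.1): "Patient will be given 90-day supply of study drug".

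Under 6.2.4.6.1 a script for the commercial product goes to the subject's "pharmacy of choice approximately 2 weeks prior to week 16 visit to ensure uninterrupted ART for the patient", and staff check that it can be obtained before the Week 16 visit. At that visit (6.2.4.7.1), "Staff will confirm with patient that they have the commercial medication".

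On counting, 5.5.1 says "Subjects will be instructed to bring all study medication in the original container at each clinic visit for drug accountability", and 5.5.2 requires all study drug, used or not, to come back to the site. Section 6.2.4.7.1, however, says that the Week 16 count comes from the container handed out at baseline.

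The count feeds two secondary endpoints: "Percentage of subjects with greater than or equal to 90% by pill count" (8.2.2.2.2, repeated in 8.7.1.2), and the comparison of survey adherence with pill counts at Weeks 4 and 16 (4.2.2.7). No formula or denominator is given. The text at hand does not say that the commercial bottle is to be brought in or counted.

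**The concern.** For up to about two weeks before the Week 16 count, a subject may hold two supplies of an identical tablet, only one of which falls under the accountability rules. At one tablet a day, every dose taken from the commercial bottle leaves one study tablet in its container. A count of study tablets cannot tell that from a missed dose.

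The error has one direction: adherent subjects can be scored as non-adherent, never the reverse. It can arise at Week 16 but not at Week 4. Pill count is the trial's only direct adherence measure that is not self-report, so it is the one check on the survey that carries the primary endpoint. In the 4.2.2.7 comparison, a truthful survey answer set against a falsely low count would look like over-reporting. With a target of 30 subjects (6.2.2.1), each subject misclassified moves the percentage at or above 90% by 1/30 = 3.3 points.

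**Working it through.** The plan states no figure to reproduce here, so the check is tablet arithmetic.

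**Inputs**
- One tablet per day (5.3.1).
- Baseline to Week 16: 16 × 7 = 112 days. Week 4 to Week 16: 12 × 7 = 84 days (6.2.4.1.2).
- Study tablets: 30 at baseline (6.2.4.4.2) and 90 at Week 4 (6.2.4.5.1), together 120.
- Commercial script about 14 days before Week 16, that is about day 112 − 14 = 98 (6.2.4.6.1).
- Cut-off: 90% or more (8.2.2.2.2).
- Assumption: *k* doses come from the commercial bottle before Week 16, with *k* from 0 to 14. The documents give no value.

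**Step 1: is the study supply short?** No. 120 − 112 = 8 tablets to spare. A subject who attends on time does not need commercial tablets before the visit.

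**Step 2: the count as literally written.** The baseline bottle holds 30 tablets, which a fully adherent subject finishes by about day 30. A commercial bottle opened from about day 98 cannot change that count. But this count says almost nothing about adherence from Week 4 to Week 16, so it cannot serve the Week 16 comparison in 4.2.2.7. It also leaves uncounted the 90 tablets issued at Week 4, which 5.5.1 requires to be brought in.

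**Step 3: the count once the Week 4 supply is included.** For a subject who misses no dose:
- days denominator: (84 − *k*)/84 or (112 − *k*)/112
- tablets-dispensed denominator: (84 − *k*)/90 or (112 − *k*)/120

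| *k* | of 84 days | of 112 days | of 90 tablets | of 120 tablets |
|---|---|---|---|---|
| 0 | 100% | 100% | 93.3% | 93.3% |
| 3 | 96.4% | 97.3% | 90.0% | 90.8% |
| 4 | 95.2% | 96.4% | **88.9%** | 90.0% |
| 5 | 94.0% | 95.5% | 87.8% | **89.2%** |
| 8 | 90.5% | 92.9% | 84.4% | 86.7% |
| 9 | **89.3%** | 92.0% | 83.3% | 85.8% |
| 11 | 86.9% | 90.2% | 81.1% | 84.2% |
| 12 | 85.7% | **89.3%** | 80.0% | 83.3% |
| 14 | 83.3% | 87.5% | 77.8% | 81.7% |

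Bold marks the first value below 90% in each column: 75/84, 100/112, 80/90 and 107/120. The third column assumes that the 30 − 28 = 2 tablets left at Week 4 are not carried forward. If they are used first, full adherence scores 82/90 = 91.1% and two commercial doses suffice (80/90 = 88.9%).

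**Step 4: how early must the bottle be opened?** With about 14 days available and daily use from opening, 9 doses need a start within 14 − 9 = 5 days of the script, and 12 doses within 14 − 12 = 2 days. On tablets dispensed, 4 doses need a start within 10 days and 5 within 9.

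**Step 5: effect of counting the commercial bottle.** Take *k* = 14 and, as an example, a commercial bottle of 30 (the pack size in 5.2.1). Study tablets used: 120 − 22 returned = 98. Commercial tablets used: 30 − 16 remaining = 14. (98 + 14)/112 = 100%, as it should be.

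**The case against.** The strongest objection is that the count as written cannot be affected. Section 6.2.4.7.1 names the baseline bottle, and Step 2 confirms that early commercial use leaves it untouched. This stands. A reader might infer that the protocol already produces a biased Week 16 count, and the text does not support that. The problem becomes live when the counting instruction is reconciled with the Week 4 dispensing, and correcting the choice of bottle alone would leave it in place.

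Second, early use is only a possibility. Section 6.2.4.6 describes availability, not a dispensing date, its purpose is continuity of treatment, and study tablets outlast the visit by eight. This also stands. The 83.3% and 87.5% figures need the commercial bottle to be filled at once and used for all 14 days. On a days denominator a few early doses do no harm.

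Third, the formula may sit in an SAP, and the medication dataset (8.3.7) holds start dates for medication taken during the study. This stands in part. The denominator can be left to an SAP, and a recorded commercial start date would help. But neither supplies a tablet count, and an SAP cannot recover tablets that nobody counted at the visit.

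Fourth, the endpoints concerned are descriptive. That is correct and limits the weight of the point. A reader might also infer that the primary endpoint is compromised. It is not, because it rests on MAAS scores alone.

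**Conclusion.** The point holds in conditional form. Commercial supply of the same tablet is arranged before the Week 16 count, and accountability covers study medication only. The Week 16 counting instruction conflicts with the Week 4 dispensing and with 4.2.2.7. When that conflict is resolved so that the Week 4 supply is counted, a fully adherent subject can be scored below 90% after 9 or 12 early commercial doses on a days denominator, or 4 or 5 on a tablets-dispensed denominator.

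This rests on two assumptions: that the reconciled count includes the Week 4 supply, and that some subjects open the commercial bottle before the visit. The size in practice is unknown. It is nil if no one does so, and at most about 14 doses per subject. Without data on the commercial bottle, the trial could not tell which case it was in. It is worth correcting because the error runs one way and is cheap to remove, but it reaches only the descriptive pill-count percentage and the survey comparison.

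**What to change.** Make the change in the same edit that reconciles 6.2.4.7 with 6.2.4.5:

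- Ask the subject to bring any commercial bottle to the Week 16 visit. The Week 14 contact in 6.2.4.6 is a natural moment to ask.
- At Week 16, record its fill date, quantity dispensed and quantity remaining.
- Compute pill-count adherence as (study tablets dispensed − returned + commercial tablets dispensed − remaining) / days in the interval. For the Week 4 to Week 16 interval, treat any baseline tablets carried forward as part of the opening stock, so that 2 + 90 − 8 = 84 for a fully adherent subject.

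Script timing and continuity of supply stay as they are, and no instruction on which supply to take is needed. The cost is one more bottle to count, at a visit where staff already ask about it, and about three CRF fields. No extra visit is required.
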